Medical history (course of disease, frequency of relapses in 1 year and 6 months before enrollment, steroid dosage)	√									
Vital signs	√	√	√	√	√	√	√	√	√	√

Items	Screening and enrollment period		Treatment and follow-up period							
	Screen (V0)	Visit 1 (V1)	Visit 2 (V2)	Visit 3 (V3)	Visit 4 (V4)	Visit 5 (V5)	Visit 6 (V6)	Visit 7 (V7)	Visit 8 (V8)	Visit 9 (V9)
Height and weight	√	√	√	√	√	√	√	√	√	√
Physical examination	√	⊙	√	√	√	√	√	√	√	√
Blood routine examination	√	⊙	√	√	√	√	√	√	√	√
Urine routine examination	√	⊙	√	√	√	√	√	√	√	√
Fasting blood glucose	√		√	√	√	√	√	√	√	√
Serum liver function	√	⊙	√	√	√	√	√	√	√	√
Blood lipid	√	⊙	√	√	√	√	√	√	√	√
Serum renal function	√	⊙	√	√	√	√	√	√	√	√
Blood EBV-DNA, and CMV antibody	√									√
24h urinary protein (>3 years old)	√	⊙	√	√	√	√	√	√	√	√
Urinary protein / creatinine	√	⊙	√	√	√	√	√	√	√	√
eGFR	√	⊙	√	√	√	√	√	√	√	√

Items	Screening and enrollment period		Treatment and follow-up period							
	Screen (V0)	Visit 1 (V1)	Visit 2 (V2)	Visit 3 (V3)	Visit 4 (V4)	Visit 5 (V5)	Visit 6 (V6)	Visit 7 (V7)	Visit 8 (V8)	Visit 9 (V9)
Tacrolimus concentration in plasma			√	√	√	√	√	√		√
Mycophenolic acid concentration in plasma			√				√			
Chest X-ray	√									√
ECG	√									√
Markers of hepatitis B and hepatitis C virus	√									
Examination of Mycobacterium tuberculosis and fungi	√									
Biological samples of blood and urine	√						√			√
Drug distribution and measurement		√	√	√	√	√	√	√	√	√
Guidance on the administration of test drug		√	√	√	√	√	√	√	√	√

Items	Screening and enrollment period		Treatment and follow-up period							
	Screen (V0)	Visit 1 (V1)	Visit 2 (V2)	Visit 3 (V3)	Visit 4 (V4)	Visit 5 (V5)	Visit 6 (V6)	Visit 7 (V7)	Visit 8 (V8)	Visit 9 (V9)
Clinical efficacy (relapse or no)			√	√	√	√	√	√	√	√
Concomitant medication	√	√	√	√	√	√	√	√	√	√
Adverse event			√	√	√	√	√	√	√	√
Record case report form	√	√	√	√	√	√	√	√	√	√

Remarks:

1. Liver function: ALT, TBiL, ALB; Renal function: creatinine, urea nitrogen, uric acid, Cystatin C;
2. Blood lipids: Triglycerides, cholesterol; Urinary protein / creatinine: morning urine; Markers of hepatitis B and hepatitis C virus: HBsAg, HBeAg, HBcAb, HCV;
3. Mycobacterium tuberculosis examination: T-sport; Fungal examination: fungal G test or other; Estimated glomerular filtration rate: $eGFR = K \times \text{height (cm)} / \text{serum creatinine (mg / dL)}$ (see Appendix);
4. Visit time window: ± 3 days for visit 2, and ± 7 days for other visits;

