4.4 Withdrawal criteria

Patients are free to withdraw from the trial at any time without any reason.

Patients must withdraw from this research in the following conditions:

- Withdrawal of the Informed Consent Form;
- Violation of the inclusion criteria or compliance with the exclusion criteria;
- No administration of the test drug according to the Protocol for 14 consecutive days due to various reasons;
- For two consecutive times, the measured value of SCr with an interval of at least 4 weeks has increased more than twice the baseline, and eGFR < 60mL/min.1.73m²;
- The target concentration of tacrolimus or mycophenolate mofetil can not be reached after dose adjustment for one month;
- ALT or total bilirubin levels reach more than 2 times of the upper limit after medication, with a continuous increase for 2 weeks; if ALT or total bilirubin levels still rise to more than 2 times of the upper limit after 2 weeks of liver protection drug treatment, stop the test drug. In case of no recovery after 2 weeks of drug withdrawal, the patient shall withdraw from the test;

- Occurrence of unknown adverse events of unacceptable nature, severity and/or duration, or occurrence of known unacceptable adverse events or the occurrence frequency exceeding expectations;
- The clinical events or safety-affecting events result in withdrawal from the clinical trial, and the investigators believe that such subjects shall withdraw from the trial;
- If pregnancy occurs during treatment, withdraw from the trial;
- Unauthorized use of drugs prohibited by this research (see "5.3 Concomitant medication");

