5.2 Administration method, dose, route and course of treatment

5.2.1 Initial administration protocol

FK506 dose: 0.05-0.10 mg/kg/day, BID

Maintained concentration: In the induction period (the first six months after treatment) (visit 2, 3, 4, 5 and 6), the trough plasma concentration of tacrolimus is 5 - 10 ng/mL;

In the maintenance period, drug dose is gradually reduced when the patient's condition is stable:

In the last six months after administration (visit 7, 8, and 9), the trough concentration is <5 ng/mL

MMF dose: 20-30 mg/kg/day, BID

Plasma concentration (AUC) [Formula: $MPA-AUC = 7.75 + (6.49 * C_0) + (0.76 * C_{0.5}) + (2.43 * C_2)$]

Maintained concentration: In the induction period (the first six months after treatment) (visit 2, 3, 4, 5 and 6)

MPA-AUC=30 - 50 µg.h/mL

In the maintenance period, drug dose is gradually reduced when the patient's condition is stable:

In the last six months after administration (visit 7, 8, and 9), MPA-AUC ≤ 40 µg.h/mL

Prednisone dose: The initial dose is 1.0-1.5 mg/kg every other day or 0.5-0.75 mg/kg every day. The dose shall be reduced after 4 weeks by 0.25 mg/kg (qd alt) or 0.125 mg/kg (every day) every 2-4 weeks. If the condition is stable, continue to reduce to 5mg (body surface area > 1 m²) and 2.5mg (body surface area < 1 m²) qd alt. Maintain at such doses until this research is completed.

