5.2.3 Dose adjustment of tacrolimus (FK506)

5.2.3.1 Adjust the dose according to the trough plasma concentration of tacrolimus. If the trough plasma concentration cannot meet the target concentration, it can be increased by adding Wuzhi capsules, ketoconazole, Hexin Shuang or cimetidine. If the trough plasma concentration of tacrolimus is >10 ng/mL, the dose of tacrolimus shall be reduced, and the trough concentration shall be rechecked after one week to adjust the target concentration. After treatment, the increase of SCr ≥ 30% of the basic value and eGFR < 60mL/min.1.73m² (excluding non-drug factors) shall prompt tacrolimus dose reduction by 50%. If the concentration still fails to reach the target after tacrolimus dose adjustment for one month, the subject shall withdraw from the trial.

5.2.3.2 If the trough plasma concentration of tacrolimus in visit 7 is ≥ 5 ng/mL, the dose of tacrolimus needs to be reduced by 20%-30%, and the trough concentration shall be rechecked in visit 8. If the trough concentration of tacrolimus is still ≥ 5 ng/mL in visit 8,

it is necessary to continue to reduce the dose of tacrolimus by 20%-30%, and recheck this concentration in visit 9.

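### The one-month off-target rule ends trial follow-up, not just study drug, and is not limited to induction: a minor point with a cheap remedy

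*Protocol*

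**What the plan says.** **Withdrawal rule.** The fifth item of the mandatory list in Protocol 4.4 reads "The target concentration of tacrolimus or mycophenolate mofetil can not be reached after dose adjustment for one month". Section 5.2.3.1 closes with the same rule for tacrolimus: "If the concentration still fails to reach the target after tacrolimus dose adjustment for one month, the subject shall withdraw from the trial". Section 5.2.4.1 has the matching sentence for MMF. None of the three names a treatment period. The SAP repeats them in 4.5.4(5), 5.2.3.1 and 5.2.4.1.

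**Maintenance levels.** Protocol 5.2.1 gives a tacrolimus trough of 5-10 ng/mL for visits 2-6, and then: "In the last six months after administration (visit 7, 8, and 9), the trough concentration is <5 ng/mL".

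**Step-down.** Under 5.2.3.2, a visit 7 trough of 5 ng/mL or more means that "the dose of tacrolimus needs to be reduced by 20%-30%, and the trough concentration shall be rechecked in visit 8". If the trough is still 5 or more at visit 8, "it is necessary to continue to reduce the dose of tacrolimus by 20%-30%, and recheck this concentration in visit 9". Withdrawal is not mentioned. SAP 5.2.3.2 has the same text, and neither document says which rule takes precedence.

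**Analysis.** SAP 8.1.2 bases efficacy on ITT principles in the FAS. SAP 8.1.3 censors a child who withdraws before completing the visits, at the date of withdrawal.

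**The concern.** Failing to hold a drug level is a reason to change or stop a drug. It does not in itself stop anyone from observing whether the child relapses. The plan nevertheless ends participation, and the primary analysis then treats the child as censored. The trigger arises after randomisation, depends on exposure to the assigned drug, and is applied by investigators who know the arm. Children who cannot be brought on target may differ in relapse risk from those who can, so the censoring may be informative. That sits badly with the ITT principle.

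The missing period limit adds a second problem. A site that applies 4.4 word for word at visit 8 removes a tacrolimus child whom 5.2.3.2 keeps. Sites could act differently. The summary would not show it, because SAP Table 3 has no discontinuation reason for an off-target level.

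The opportunity to trigger the rule is also uneven. The flow chart row "Tacrolimus concentration in plasma" is marked at visits 2-7 and 9, while the mycophenolic acid row is marked at visits 2 and 6 only. Section 5.2.4.2 requires no retest after the visit 6 reduction.

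**Working it through.** **1. The plan's own figures.** Inputs are 1-year relapse-free survival of 0.56 (MMF) and 0.70 (tacrolimus), 2 years of accrual and 3 years in total (Protocol 3.3.2, Appendix 4). On constant hazards, HR = ln 0.70 / ln 0.56 = 0.6151, as Appendix 4 states. Uniform accrual with 114 and 115 children gives 133.7 expected events against 133.8 stated. 229/0.85 = 269.4, rounded up to 270. The sample size is not at issue; the constant-hazard scale is reused below.

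**2. Is one month already past at visit 8?** Visits 7, 8 and 9 are at Days 224, 280 and 364, each ±7 days.
- Visit 7 to visit 8: 280 - 224 = 56 days; with windows 273 - 231 = 42 to 287 - 217 = 70.
- At every permitted date a child still at 5 ng/mL or more at visit 8 is beyond one month of adjustment, so the literal 4.4 condition is met.

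**3. Which children would that be?** If level is proportional to dose (assumed), a 20% cut leaves a trough of 5 or more when the visit 7 value was at least 5/0.8 = 6.25 ng/mL. For a 30% cut the limit is 5/0.7 = 7.14 ng/mL.

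**4. Observation at stake per child.** Visit 8 to visit 9: 364 - 280 = 84 days; with windows 357 - 287 = 70 to 371 - 273 = 98. 84/364 = 23.1% of the observation period.

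**5. Relapses not recorded.** Planned tacrolimus hazard, 135 children, before loss:
- Relapse-free at Day 280: 0.70^(280/364) = 0.760; 0.760 × 135 = 102.6 children.
- Relapse from Day 280 to Day 364: 1 - 0.70^(84/364) = 0.0790.
- The share withdrawn is not in the documents; 5% to 20% is assumed. Children: 0.05 × 102.6 = 5.1 to 0.20 × 102.6 = 20.5. Unrecorded relapses: 5.1 × 0.0790 = 0.4 to 20.5 × 0.0790 = 1.6.
- Planned first-year events: 0.44 × 135 + 0.30 × 135 = 99.9. The loss is 0.4% to 1.6% of these.

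**6. Error in the tacrolimus 1-year Kaplan-Meier estimate.** Suppose the withdrawn children have relapse probability q over the last 84 days and the others have 0.0790. Then error (estimate minus truth) = 0.760 × share × (q - 0.0790). With half the planned hazard (assumed), q = 1 - 0.70^(0.5 × 84/364) = 0.0403. With double (assumed), q = 1 - 0.70^(2 × 84/364) = 0.1518.

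| Share withdrawn | Half hazard | Double hazard |
|---|---|---|
| 5% | -0.15 points | +0.28 points |
| 20% | -0.59 points | +1.11 points |

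The planned difference is 0.70 - 0.56 = 14 points.

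**7. What this leaves out.** Steps 2 to 6 size only tacrolimus withdrawals at visit 8. The rule can also act in induction, in either arm, and each such withdrawal would cost more follow-up. The documents give nothing from which to count those.

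**The case against.** The strongest reply is that the visit 8 conflict disappears on a sensible reading, and most of that reply stands.
- Section 5.2.3.1 is written around the induction range. It corrects a missed target by raising the level and acts on the high side only above 10 ng/mL, after which "the trough concentration shall be rechecked after one week to adjust the target concentration". None of this suits a ceiling of 5 ng/mL.
- Section 5.2.3.2 follows directly, with its own trigger and rechecks. Under the literal reading of 4.4 its visit 8 instruction could never operate.
- The flow chart schedules no routine tacrolimus level at visit 8; that level exists because 5.2.3.2 orders it.
- Section 5.2.1 introduces the lower level with a sentence beginning "In the maintenance period, drug dose is gradually reduced when the", which describes a taper, and does not call it a target.

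A reader might therefore infer that the protocol orders the removal of these children. The documents do not support that. What is missing is a sentence of precedence.

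A reader might also infer that only the tacrolimus arm can lose children to the rule. That goes too far. Section 5.2.4.1 carries the same rule for MMF and leaves levels after a dose adjustment to the investigator, so an unscheduled MMF level could trigger it. The schedule makes a maintenance-phase trigger much more likely under tacrolimus, but not exclusive to it.

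Nor does the plan abandon drop-outs. Protocol 4.5.2 requires contact with them, completion of whatever evaluations are possible, and retention of their data for analysis. It does not require visits to Day 364, and SAP 8.1.3 still sets the censoring date at withdrawal.

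Finally, censoring at withdrawal applies to every reason in 4.4. That is true. This reason, however, concerns drug exposure alone, and unlike withdrawn consent it does not prevent further observation.

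**Conclusion.** The point holds as a minor, inexpensive improvement. Its substance is that a missed drug level forces the child out of the trial, and the primary analysis censors the child there despite its stated ITT principle. The lack of a period limit is secondary, since 5.2.3.2 very probably governs visits 7-9.

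For the visit 8 cases, the error in the tacrolimus 1-year estimate is about 1 percentage point at most. That upper end needs a 20% share and a doubled hazard together, and every site applying 4.4 literally. The share, the hazard ratios and the proportionality of level to dose are assumptions. The true share may be low, because the taper can begin after visit 6, 224 - 168 = 56 days before visit 7.

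It would be tempting to conclude that the rule favours tacrolimus or endangers the primary result. Neither can be shown: the sign depends on whether the withdrawn children relapse more or less than the rest, on which the documents are silent, and the size found here is small against 14 points.

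**What to change.** 1. In Protocol 4.4 (fifth item), 5.2.3.1 and 5.2.4.1, and in SAP 4.5.4(5), 5.2.3.1 and 5.2.4.1, make the one-month rule a stop of study drug, not of trial participation, in both arms.
2. Keep recording relapse for these children at the scheduled visits to Day 364. Amend SAP 8.1.3 so that their relapses count in the FAS primary analysis and they are not censored at the stop of drug.
3. Add one sentence in both documents that 5.2.3.2 governs tacrolimus levels at visits 7-9.

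The cost is one or two sentences at each place and a few retained visits that are already scheduled. Some children will be analysed after a change of treatment, which is what an ITT analysis accepts; the PPS remains available for the on-treatment question. SAP 4.1 describes enrolment as completed. If follow-up has ended too, the SAP change is still useful for any relapse status obtained after withdrawal.

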4.1 Inclusion criteria

Only those who meet all the conditions listed in this column can be considered for inclusion in this research:

- (1) Steroid-sensitive nephrotic syndrome with frequent relapse (FRNS) or steroid dependence (SDNS);
- (2) Age: 2-18 years old;
- (3) Normal renal function: $eGFR \geq 90 \text{ mL/min/1.73m}^2$;
- (4) At the time of enrollment, urinary protein $< 1+$ or urinary protein/creatinine $< 0.2 \text{ g/g}$ ($< 20 \text{ mg/mmol}$) in the morning for 3 consecutive days or more;
- (5) No use of tacrolimus, mycophenolate mofetil, cyclosporine A, rituximab or cyclophosphamide within 2 years before enrollment;

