4.2 Exclusion criteria

Anyone with one of the following conditions cannot be included in this research:

- (1) Steroid-resistant nephrotic syndrome (SRNS);
- (2) Family history of nephrotic syndrome, chronic glomerulonephritis or uremia;
- (3) Leukopenia (leukocyte $\leq 3.0 \times 10^9/\text{L}$);
- (4) Moderate and severe anemia (hemoglobin $< 9.0 \text{ g/dL}$);
- (5) Thrombocytopenia (platelet count $< 100 \times 10^{12}/\text{L}$);

- (6) Those with positive HBV serological indexes (HBsAg or/and HBeAg or/and HBcAb), positive HCV or abnormal liver function (ALT or total bilirubin exceeding 2 times or more of the upper limit, with a continuous increase for 2 weeks);
- (7) There are chronic active infections such as Epstein-Barrvirus, cytomegalovirus or Mycobacterium tuberculosis, and the usage of steroids and immunosuppressive agents may aggravate the state of an illness;
- (8) Secondary nephrotic syndrome (such as purpura nephritis ,lupus nephritis,etc);
- (9) Those who with hematological or endocrine system diseases as well as serious organs illness such as heart, liver or kidney;
- (10) Other autoimmune diseases or primary immunodeficiency or tumors;
- (11) Those who was known be sensitized to tacrolimus, mycophenolate mofetil, glucocorticoids or any ingredient of the above drugs;
- (12) Those who have participated in other clinical trials within three months before enrollment;
- (13) Those who was not suitable for participating this study judged by investigator;

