It refers to the local tissue inflammatory reaction and systemic inflammatory reaction caused by bacteria, viruses, fungi, parasites and other pathogens invading the human body. Serious life-threatening infections, such as meningitis and infective endocarditis, are occasionally reported, and some evidences show that certain types of infections, such as conjugated and atypical waste bacilli infections, lay have a high incidence

Gastrointestinal adverse reactions

Gastrointestinal adverse reactions include nausea, vomiting, dyspepsia, abdominal pain, constipation, upper and lower gastrointestinal discomfort, gastrointestinal inflammation, gastroduodenal ulcer, gastrointestinal bleeding and perforation, etc. Colitis (sometimes caused by cytomegalovirus), pancreatitis, and individual cases of intestinal villus atrophy.

Blood system and immune system

In patients treated with this product in combination with other immunosuppressants, pure red cell aplasia (PRCA) and hypogammaglobulinemia have been reported.

Congenital diseases

Congenital malformations, including ear, face, heart and nervous system abnormalities, have been reported in the children of mothers treated with this product and other immunosuppressants during pregnancy. There are also reports of spontaneous abortion in early pregnancy.

Pregnancy, puerperium and perinatal periods

Spontaneous abortion has been reported in patients (mainly in early pregnancy) exposed to mycophenolate mofetil.

Malignant tumors

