8.2 Definition of serious adverse event

Serious adverse event (SAE) refers to the AE occurring at any stage of this research (i.e. screening period, follow-up period) and complying with one or more of the following criteria:

- Causing death
- Immediate life-threatening
- Requiring hospitalization or extension of the original length of stay
- Causing sustained or significant deformity/disability, or seriously impairing the ability to complete normal life functions
- Congenital malformation or defect at birth
- An important medical event that may cause harm to the patient or may require medical intervention to prevent one of the above outcomes

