8.3 Records of adverse events

The information of AEs to be collected in this research includes the following aspects:

- Endpoint event
- Adverse events related to the test drugs (according to the judgment of the investigators)
- Serious adverse event

Cycle of adverse event collection

The collection of AEs and adverse drug reactions (DAEs) of concern will be carried out throughout this research, from randomization to site close-out visit (SCV, included).

SAE records will be carried out throughout this research, from the time of signing the Informed Consent Form to SCV (included).

Follow-up of unresolved adverse events

If any AE, DAE and SAE of concern remain unresolved at the patient's last study visit, the investigators shall follow up these events in accordance with the medical instructions as required for medical needs in this research, but it is not necessary to record further in the electronic case report form (eCRF). If deemed necessary, the Sponsor reserves the right to obtain the additional information on unresolved AE/SAE of concern.

Variables

For each non-serious AE and DAE of concern, the following variables will be collected:

- AE (verbatim record);
- AE start and end dates;
- Maximum intensity;

- Whether the AE is serious;
- The investigators' assessment of the causal relationship with the test drug (yes or no);
- Measures and outcomes taken for the test drug

In addition, the following variables will be collected for SAE:

- Date when AE meets SAE criteria;
- Date when the investigators find SAE;
- Reasons for classifying AE as SAE;
- Date of admission;
- Date of discharge;
- Possible causes of death
- Date of death;
- Autopsy performed (if any);
- Autopsy results
- AE description
- Assessment of causality with this research procedure;
- Assessment of causality with the other drugs

It is important to distinguish serious AE from severe AE. Severity is the index of intensity evaluation, while seriousness is defined according to the criteria in Section 8.2. AE with severe intensity is not necessarily serious. For example, nausea for several hours may be considered as severe nausea, but not SAE. On the other hand, a stroke that results in only a limited degree of disability may be considered as a mild stroke, but should be considered as SAE.

The definition of intensity classification is as follows:

1. Mild (signs or symptoms are felt but easily tolerated)

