8.4 Report of serious adverse events

All SAEs must be reported, regardless of whether they are considered to have causalities with the test drugs or study procedure. All SAEs will be recorded in eCRF.

In case of any SAE during this research, the investigators or other staff of the center shall notify the relevant Sponsor representative immediately or no later than 24 hours after learning of the event.

The designated Sponsor representative shall work with the investigators to ensure that all necessary information is provided to the Sponsor's patient safety data entry center within 1 working day after the first receipt of fatal and life-threatening events and 5 working days after the first receipt of all other SAEs.

For fatal and life-threatening AEs, if important or relevant information is missing, immediate active follow-up is required. The investigators or other staff of the center shall notify the Sponsor representative of any follow-up information about the previously reported SAE immediately or no later than 24 hours after receiving the information.

If the Web-based data collection (WBDC) system is not available, the investigators or other staff of the center shall report SAE to the appropriate Sponsor representative by telephone, noting that the same reporting window (24 hours) is still applicable.

If initial or subsequent reporting is made through the means other than WBDC system, the investigators must finalize any SAE information into the eCRF through WBDC system as soon as this system is enabled again.

9. Quality control and assurance of the trial

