9.5. Safety analysis (SS)

9.5.1. Adverse event (AE)

Table 62. Between-group comparison of AE

Items	Experimental group			Control group			P-value
	No. of AEs	No. of subjects	Percentage	No. of AEs	No. of subjects	Percentage	
AE							
AE of severe severity							
Drug-related AE							
Serious adverse event (SAE)							
Drug-related SAE							
Drop-out due to AE							
Drop-out due to SAE							

Note 1: The definitions related to drugs are “definitely related”, “probably related”, “possibly related”, “unlikely related” and “not related”.

Note 2: The data of SAE that cause the drop-out came from the external file “XX”.

Table 63. characteristics of AE in each group

Items	Experimental group			Control group			P-value
	No. of AEs	No. of subjects	Incidence	No. of AEs	No. of subjects	Incidence	
Relationship with study drug							
Definitely related							
Probably related							

Items	Experimental group			Control group			P-value
	No. of AEs	No. of subjects	Incidence	No. of AEs	No. of subjects	Incidence	
Possibly related							
Unlikely related							
Not related							
Outcome	Recovered/resolved						
	Recovered/resolved with sequelae						
	Not recovered						
	Recovering/resolving						
	Death						
	Unknown						

Table 64. Between-group comparison of SAE

Items	Experimental group (n=XX)			Control group (n=XX)			Total (n=XX)	P-value
	No. of AEs	No. of subjects	Incidence (%)	No. of AEs	No. of subjects	Incidence (%)		
Results in death								
Requires hospitalization								
Prolongs hospitalization								
Disability								
Dysfunction								
Congenital malformation								
Life threatening								
Other								

Table 65. Summary of AE base on SOC and PT coding

Indicator	Experimental group (n=XX)			Control group (n=XX)			Total (n=XX)	P-value
	No. of AEs	No. of subjects	Incidence (%)	No. of AEs	No. of subjects	Incidence (%)		
AE								

Indicator	Experimental group (n=XX)			Control group (n=XX)			Total (n=XX)			P-value
	No. of AEs	No. of subjects	Incidence (%)	No. of AEs	No. of subjects	Incidence (%)	No. of AEs	No. of subjects	Incidence (%)	
SOC1										
PT1										
PT2										
...										
SOC2										
PT1										
PT2										
...										

Table 66. Summary of adverse reactions base on SOC and PT coding

Indicator	Experimental group (n=XX)			Control group (n=XX)			Total (n=XX)			P-value
	No. of AEs	No. of subjects	Incidence (%)	No. of AEs	No. of subjects	Incidence (%)	No. of AEs	No. of subjects	Incidence (%)	
Adverse event										

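### Pregnancy forces withdrawal, but no exclusion names it and no pregnancy test is scheduled, so an unrecognised pregnancy could be randomised to MMF

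*Protocol*

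**What the plan says.** Protocol 4.1 admits children by age with no restriction by sex: "Age: 2-18 years old". Protocol 4.4 makes withdrawal compulsory for a list of conditions, one of which reads "If pregnancy occurs during treatment, withdraw from the trial"; SAP 4.5.4 item (9) repeats it. The reason is in Protocol 8.1.2, on MMF: "Congenital malformations, including ear, face, heart and nervous system abnormalities, have been reported in the children of mothers treated with this product" (taken while pregnant, alongside further immunosuppressive drugs). The same section reports spontaneous abortion, mainly early in pregnancy.

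The exclusions in Protocol 4.2 and SAP 4.5.2 run from (1) to (13). The only one that could cover pregnancy is the last: "Those who was not suitable for participating this study judged by investigator". The flow charts (Protocol 1.3, SAP 4.4) list the procedures from V0 to V9, and none is a pregnancy test.

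On outcomes, Protocol 8.2 counts "Congenital malformation or defect at birth" as a serious adverse event. Under 8.4, staff must "notify the relevant Sponsor representative immediately or no later than 24 hours after learning of the event". The SAP has a congenital malformation row in "Table 64. Between-group comparison of SAE". Protocol 8.3 records serious events until site close-out. It tells investigators to follow events unresolved at the last visit as medically needed, without further eCRF entry, and lets the sponsor ask for more information.

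**The concern.** The plan stops treatment for pregnancy but does not look for it, either at entry or later. The withdrawal rule concerns pregnancy arising on treatment and works only once someone reports or notices it. Its companion rule, withdrawal for meeting an exclusion criterion, cannot catch a pregnancy present at entry, because pregnancy is not a named exclusion. The risk that the protocol itself describes lies mainly in early pregnancy, when the girl, her family and the investigator may not yet know. What is at stake is fetal harm that cannot be undone, in a trial where the drug concerned is assigned by randomisation. This is a question of participant safety, not of bias in the efficacy comparison.

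**Working it through.** There is no planned figure to reproduce. The check is a comparison of lists.

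**Entry.** Exclusions (1) to (13) cover steroid resistance, family history, three blood-count limits, hepatitis or abnormal liver function, chronic infection, secondary disease, organ disease, autoimmune disease or tumour, drug allergy, recent trial participation and investigator judgement. Pregnancy is named in 0 of 13.

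**Testing.** Visits V0 to V9 make 10. Pregnancy-test rows: 0 in the protocol chart and 0 in the SAP chart. Urine routine examination is required at V0 and at V2 to V9, which is 1 + 8 = 9 visits, and is optional at V1. Screening may fall up to 30 days before entry, so a screening test alone could miss a pregnancy that begins before the first dose. SAP Table 6 counts gestations and parturitions, but beside birth weight and dystocia. These look like the child's own birth history, not a pregnancy check.

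**Exposure.** Allocation is 1:1, so a girl who enters with an unrecognised pregnancy has probability 1/2 of receiving MMF. The documents do not give the number of post-menarchal girls. The protocol's Background says that the disease mostly occurs at age 2-6 and that the male-to-female ratio is about 3:2, so the number is probably small.

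**Outcome of a pregnancy.** Serious events are recorded to site close-out, whose date is not given. Protocol 15.3 puts the end of observation at July 2022. Assume that close-out is no earlier and that gestation lasts about 9 months. Then July 2022 minus 9 months is October 2021, so a pregnancy conceived before about that date would reach term inside the recording window, and a later one might not. Protocol section 16 sets one month of follow-up after treatment, for subjects who had adverse events. Drop-out contact under 4.5.2 covers reasons, last medication time and feasible evaluations. None of these provisions says that a known pregnancy is followed to its outcome.

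**Potassium (separate minor note).** Protocol 8.1.1 lists hyperkalemia as very common on tacrolimus, on the same line as hyperglycemia. Fasting glucose is scheduled at 9 visits and has SAP Tables 50 and 93. Potassium is in no panel defined in the flow-chart remarks. It is also absent from change Tables 41-50 (10 tables) and shift Tables 82-98 (17 tables). Serum is already required at V0 and V2 to V9, so adding potassium means at most 9 x 270 = 2,430 values.

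**The case against.** The strongest objection is that safeguards exist and few girls are affected. An investigator can exclude a known pregnancy under item (13), and withdrawal is compulsory once a pregnancy is known. The consent pages were removed before review, so contraception advice there cannot be ruled out. All of this stands. But advice is neither an exclusion nor a test, and judgement cannot act on a pregnancy that nobody has tested for.

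A reader might infer that the plan abandons a girl once she is withdrawn for pregnancy. The documents do not support that. Protocol 8.3 requires medically needed follow-up of unresolved events, keeps the sponsor's right to further information and records serious events to site close-out. A birth defect that comes to light has a reporting duty and a table row. What is missing is narrower: an explicit rule that the outcome be sought.

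A reader might also infer that hyperkalemia could never appear in the results. That too goes too far. Protocol 8.3 requires the listed reactions to be collected, Protocol 11.3.6 and SAP 8.1.6 count clinically significant laboratory changes as adverse events, and SAP Tables 65-66 would show them. The SAP also tabulates analytes outside the protocol's defined panels, such as AST and globulin, so sites evidently measure more than the remarks list. The remaining point is that potassium testing is left to the site's choice. Trough targets, eGFR of at least 90 at entry, scheduled creatinine and the bar on ACE inhibitors and ARBs for hypertension may limit severity, and 8.1.1 describes the listed reactions as reversible or reducible.

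**Conclusion.** The pregnancy point holds. Followed as written, the plan could randomise an unrecognised pregnancy to MMF: 0 of 13 exclusions name pregnancy and 0 tests are scheduled over 10 visits. The change should be made because the possible harm is grave and the remedy cheap, even though few girls are likely to be affected. The conclusion rests on the eligibility lists and flow charts as published and assumes nothing about the removed consent pages.

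The lack of an explicit pregnancy-outcome rule is a lesser, related gap. Potassium is a separate minor monitoring point. In an open-label trial, discretionary testing could differ between arms, but the documents give no basis for sizing any such difference. It would be wrong to infer that the trial's main result is at risk: neither part touches the primary analysis, power or sample size.

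**What to change.** 1. Add pregnancy to the exclusions in Protocol 4.2 and SAP 4.5.2.
2. Add a urine pregnancy test for post-menarchal girls in both arms: at screening, at V1 before the first dose (preferably before the randomisation envelope is opened, since pregnancy would then be an exclusion) and at treatment visits. Use the urine already collected, and make the optional V1 sample required for these girls.
3. State in Protocol section 8 that the outcome of any pregnancy is to be reported, including after withdrawal.
4. Check that the consent form gives contraception advice, because a visit test detects a pregnancy but does not prevent one.

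The cost is a small assay charge for a probably small subgroup and later contact with any girl withdrawn for pregnancy. No extra visits are needed.

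As a low-cost option for the minor note, add potassium to the serum already drawn at screening and V2 to V9 in both arms, with one change-from-baseline table and one shift table. That is at most 2,430 values.
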